8.2 Permitted medications

Vaccines that are available to study participants including but not limited to COVID-19, influenza and pneumonia vaccines.

8.3 Prohibited Medications including approved and non-approved medications for IPF

8.3.1 Medications approved for IPF

- Nintedanib
- Pirfenidone

Following the most recent DSMB recommendation, the above approved medications for IPF are prohibited in GALACTIC-1, and if taken, should result in immediate exclusion from screening for the study, or withdrawal from the study treatment.

Under caring physician's medical judgement, if deemed appropriate, patients with IPF may discontinue nintedanib or pirfenidone and be considered for screening after a wash out period of minimum 7 days.

Following randomization, study participants are only permitted to take nintedanib or pirfenidone after withdrawals of the inhaled study treatment.

8.3.2 Non-approved medications for IPF

Current guidelines recommend against use of a number of drugs, either alone or in combination, to modify disease progression in idiopathic pulmonary fibrosis, and the use of the following should be result in exclusion from the study:

- N-acetylcysteine
- Azathioprine
- Ambrisentan

- Bosentan
- Macitentan
- Mycophenolate mofetil
- Warfarin (disallowed only when prescribed solely for the treatment of IPF and is permitted for other recognised indications such as Atrial Fibrillation)

8.4 Management of Clinical Events

Management of all types of adverse events, regardless of the possible underlying cause is the responsibility of the treating physician/investigator.

8.5 Blinding and Unblinding procedures

8.5.1 Blinding

This study is a double-blind study which will be maintained throughout the study, including the follow-up period. Study medication is identified by a medication code number. Packaging and labelling will be otherwise identical. Subjects, Investigators and everyone involved in analysing or with an interest in this double-blind study (Sites, Study team, CROs, other service providers) will remain blinded with regard to the randomised treatment assignments until after database lock. Only the DSMB will have access to unblinded information. An IVRS/IWRS will be used to assign subjects to treatment groups at study start. The randomisation code will be kept undisclosed up to database lock.

8.5.2 Unblinding

If the Investigator believes that knowledge of the IMP received by a subject is essential for appropriate treatment of an AE, the Investigator should ideally consult with the CRO/Galecto before breaking the code. In any event, the Investigator should inform Galecto Biotech AB (subsequently referred to as Galecto) as soon as possible whenever the code has been broken for a subject. In the event that the site requires emergency access to an individual subject code and personnel from Galecto are not available, each site may break the blind without any prior consultation. In such an event, the Chief Investigator, Principal Investigator or delegate would

notify Galecto as soon as possible *via* email or fax. If the Investigator needs to break the blind for an individual subject, the date and reason will be recorded in the subject's CRF. The IVRS/IWRS will provide a telephone/web procedure for unblinding the code to the Investigator / Pharmacist / investigational drug storage Manager. The Investigator will not reveal the unblinded treatment code to any other member of the clinical team involved in the study or to the Study Monitor. If the code is broken for any individual subject, the subject will be withdrawn from the study and the procedures accompanying the withdrawal visit performed. If the code is broken without justification, this will be deemed a serious protocol violation.

To avoid unblinding of the study team through drug safety reports which are to be unblinded as per regulatory requirements, a procedure will be maintained to keep code-breaking in these cases unknown to the study team.

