6.2 Number of Participants

Approximately 141 participants in total will be randomized in GALACTIC-1.

Participants are considered evaluable if they have taken at least one dose of the double-blind treatment.

Participants who prematurely discontinue double-blind study treatment after randomization can remain in the study and complete the remaining scheduled visits, if possible.

Any participants who withdrawn from the study after randomization cannot be replaced and re-screened.

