10.3.1 Screening & Randomisation

After giving his/her Informed Consent, the patient may be selected based on inclusion and exclusion criteria for the study at visit 1. The shipment or transfer of HRCT for review can be

organised before the screening visit provided the participant has given and signed his Informed Consent. The screening is up to 6 weeks.

The participants will be randomised at visit 2 if all inclusion and exclusion criteria are fulfilled. The results of laboratory parameters from visit 2 may only become available 24 to 72 hours after visit 2. Therefore, laboratory results from visit 2 cannot qualify as exclusion criteria. However, in case these results would retrospectively fulfil an exclusion criterion, the patient will be withdrawn unless continuation is justified in writing by the Investigator.

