14.6 Determination of Sample Size

The null hypothesis for the treatment difference between GB0139 at 3 mg and placebo for the two doses is tested using a type I error of 10% for a 2-side test. The power for detecting a statistically significant difference in the treatment effect (annual rate of decline in FVC or the FVC change from baseline to 52 weeks) is dependent on the effect size (mean treatment difference/ standard deviation) and the number of subjects per treatment group.

To detect an average difference from placebo in decline in FVC of at least 100 ml and with a standard deviation of 240 ml then a final sample size of 141 subjects would provide 75% power, assuming that future subjects are randomised into the study on a 1:2 randomisation allocation so that for every subject randomised to placebo 2 subjects will be randomised to 3 mg GB0139.

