14.7 Randomization

Following the Protocol version 6.1_UK participants will be randomised in blocks to double-blind treatment in a 1:2 ratio (Placebo : GB0139 3 mg). The unbalanced randomisation is to maintain the same probability of allocation to placebo post-Protocol version 6.1_UK since this may impact participant enrolment. Note that prior to Protocol version 6.1_UK participants were randomized in blocks to double-blind treatment in a 1:1:1 ratio (GB0139 3 mg : GB0139 10 mg : Placebo) stratified by SoC.

The Sponsor will arrange for the randomization and the packaging and labelling of trial medication. The randomization list will be generated using a validated system, which involves a pseudo-random number generator so that the resulting treatment will be both reproducible and non-predictable. The block size will be documented in the CTR. Access to the codes will be controlled and documented.

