14.8 Handling of Missing Data

This section describes the estimands approach for the primary analysis and associated sensitivity analyses using the Detailed Clinical Objectives framework described by Bell [51].

The trial will compare GB0139 3 mg with Placebo in patients with IPF not currently treated with pirfenidone or nintedanib. The primary objective is to demonstrate superiority of GB0139 3 mg for the mean annual rate of decline in FVC in mL. A composite strategy will be taken to patient deaths with FVC attributed the lowest value recorded in the trial when a patient dies.

Three specific inter-current events (ICEs) are anticipated during the trial: death, treatment discontinuation, and initiation of pirfenidone or nintedanib. The handling of these ICEs for the treatment effect of primary interest and planned sensitivity analyses for the primary endpoint are described in [Table 5](#).

Table 5: Handling of anticipated ICEs for treatment effect of primary endpoint

Treatment effect	Description	Death	Treatment discontinuation	Initiation of IPF therapy
Primary (ICEs of treatment discontinuation or additional IPF therapy)	Randomized and treated patients with treatment policy applied for intercurrent events other than death	FVC attributed the lowest value recorded in the trial when a patient dies	Analysis will include all available FVC measurements after randomised treatment discontinuation	Analysis will include all available FVC measurements after initiation of additional IPF therapy
Sensitivity 1 (on-treatment)	Randomized and treated patients while on randomised treatment	FVC attributed the lowest value recorded in the trial when a patient dies	Analysis will exclude any FVC measurements after randomised treatment discontinuation	Analysis will exclude any FVC measurements after initiation of additional IPF therapy
Sensitivity 2 (ICE of Death)	Randomized and treated patients while on	FVC attributed value of 0	Analysis will exclude any FVC measurements after	Analysis will exclude any FVC measurements after

	randomised treatment	when a patient dies	randomised treatment discontinuation	initiation of additional IPF therapy

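### A code break takes the subject out of the study and not only off study drug, so follow-up that the treatment-policy analysis relies on is lost by rule

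*Protocol*

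**What the plan says.** On code breaks, Protocol 8.5.2 (Unblinding) is unconditional: "If the code is broken for any individual subject, the subject will be withdrawn from the study". The same sentence calls for the withdrawal-visit procedures, which under note 9 of the schedule in 2.2 include FVC, DLCO and 6MWT. Section 10.6 then rules out collecting or adding any new information on a subject who has left the study.

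On stopping study drug, the plan takes a different line. Section 6.2: "Participants who prematurely discontinue double-blind study treatment after randomization can remain in the study". Section 10.5 says the same, subject to the investigator's medical judgement. For the primary estimand, Table 5 in 14.8 applies treatment policy to every intercurrent event except death, and for stopping drug it says: "Analysis will include all available FVC measurements after randomised treatment discontinuation". Section 14.4.1 includes retrieved dropout measurements and assumes that what is still missing is missing at random. Section 14.4.2 sets an intent-to-treat principle for the secondary endpoints. Code break appears neither among the intercurrent events in 14.8 nor as a named reason for withdrawal in 10.6.

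For hospitalisation and death, SAP 7.2.3.3 and 7.2.3.4 censor a discontinued subject without an event at the earlier of study discontinuation and Day 379.

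For a Visit 2 laboratory result that turns out to meet an exclusion criterion, Protocol 10.3.1 says: "the patient will be withdrawn unless continuation is justified in writing by the Investigator". It does not say whether this means withdrawal from study drug or from the study.

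**The concern.** A treatment-policy estimand needs outcomes after the intercurrent event. Under 8.5.2 and 10.6 together, a code break guarantees that those outcomes are not collected, although the visits are already on the schedule.

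The subjects concerned are not a random sample. Section 8.5.2 links a code break to an adverse event whose treatment is thought to require knowing the assignment, so later lung function and event risk may well differ from those of other subjects in the arm. The primary model would project their FVC under missing at random, and the Cox models would treat their censoring as uninformative. If affected subjects on active go on to do worse than the model projects, the drug looks better than it is.

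**Working it through.** **1. What is lost and what is kept after a code break**

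| Data | Kept | Lost |
|---|---|---|
| FVC | Earlier visits and one withdrawal-visit value | All later scheduled visits |
| SGRQ | Earlier visits | Everything later; not scheduled at the withdrawal visit (2.2) |
| Hospitalisation, death | SAEs to 30 days after last dose, then only related SAEs (Protocol 11.3); a phone call 7 to 14 days after the withdrawal visit (10.3.4) | Other later events up to Day 379 |

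Even the items kept after withdrawal under 11.3 and 10.3.4 do not fit a literal reading of 10.6. The SAP takes the date of death from the study-completion form, and the documents do not say how a death reported after withdrawal would reach that form.

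**2. Whether the planned sensitivity analysis repairs this**

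SAP 7.2.2.4 makes the multiple imputation conditional on concern about the amount of missing data. SAP 11.3 builds the imputation from subjects who stopped drug early but still had FVC at Week 52. A code-broken subject withdrawn earlier cannot belong to that group. The imputation therefore borrows from subjects without a code break and assumes that their reasons for stopping are similar.

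**3. The plan's own figure**

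Inputs from Protocol 14.6: difference 100 mL and "with a standard deviation of 240 ml then a final sample size of 141 subjects would provide 75% power", "tested using a type I error of 10% for a 2-side test". The 1:2 allocation in 14.7 splits 141 into 47 placebo and 94 active.

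- SE = 240 × √(1/47 + 1/94) = 42.9 mL
- 100 / 42.9 = 2.332; 2.332 − 1.645 = 0.687; power = Φ(0.687) = 75.4%
- A noncentral t calculation gives 75.1%

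The stated 75% reproduces. It contains no dropout allowance, and 6.2 does not allow withdrawn subjects to be replaced.

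**4. Power cost**

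Treat each affected subject as wholly lost, which overstates the cost because earlier FVC still enters the slope model:

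- 1 lost: 75.2%
- 3 lost: 74.6%
- 5 lost: 74.1%
- 14 lost (10%): 71.5%

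This is about 0.3 points per subject, so sample size is not the issue.

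**5. Possible bias**

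The documents give neither the number of code breaks nor the later decline of such subjects, so both are assumptions. Let k be the excess of affected subjects on active (taken here as k on active and none on placebo), and let e be their yearly decline beyond what the model projects. Bias in the active mean ≤ (k / 94) × e.

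| k | e = 200 mL/year | e = 400 mL/year |
|---|---|---|
| 1 | 2.1 mL | 4.3 mL |
| 3 | 6.4 mL | 12.8 mL |
| 5 | 10.6 mL | 21.3 mL |

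These are ceilings for the stated inputs, because they charge a full year of excess decline and ignore the earlier and withdrawal-visit FVC. If the excess began at Week 26, the k = 3, e = 400 entry would be 3/94 × 400 × 0.5 = 6.4 mL. An affected placebo subject would shift the comparison the other way by e/47, twice the weight of one active subject. For scale, e = 400 is twice the whole 200 mL placebo decline assumed in the synopsis. The figure 94 is the planned 2:1 split; a smaller active arm would raise the entries in proportion.

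**The case against.** The strongest reply is that there is no outright contradiction. Sections 6.2 and 10.5 are permissive, Table 5 uses only the FVC that is available, and 8.5.2 can be read as a specific exception. That is fair as to wording. It does not rescue the design: an exception that forbids retrieval still undercuts an estimand and a primary analysis that depend on it, and nothing in 14.8 acknowledges the exception.

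A second reply is that data after unblinding may be biased. Some of this stands, most clearly for SGRQ if the subject learns the assignment. But 8.5.2 restricts disclosure of the code, 10.4.13 has spirometry evaluated centrally, and death is objective. FVC after unblinding can be set aside in a sensitivity analysis only if it was collected.

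A third reply is that the withdrawal sentence is the only text in 8.5.2 on what happens to the subject afterwards, so changing it would leave study-drug status undefined. This stands, and the fix allows for it.

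Four stronger readings are tempting, and the documents do not support them:

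- **That all post-event data vanish.** One withdrawal-visit FVC and the SAE window remain.
- **That code breaks follow serious events, mostly on active drug.** Section 8.5.2 speaks of an adverse event, and nothing indicates an imbalance between arms.
- **That a Visit 2 laboratory result also removes the subject from the study.** Section 10.3.1 does not say from what the patient is withdrawn, and it allows a written exception. None of the 16 exclusion criteria sets a haematology or chemistry threshold, and a baseline sample is unlikely to depend on treatment. The defect there is ambiguity. It still matters: results can arrive 24 to 72 hours after the visit at which the first dose is given, so such a subject is in the mITT set and cannot be replaced.
- **That a figure such as 13 mL estimates the bias.** It is one cell of an assumed range.

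**Conclusion.** The point holds for code breaks. Sections 8.5.2 and 10.6 together remove follow-up that Table 5, 14.4.1 and 14.4.2 presuppose, in subjects whose missing data may be informative, and the conditional imputation analysis does not fill the gap.

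The effect is probably small. Power falls by about 0.3 points per subject wholly lost. Bias in the active mean is at most about 2 to 21 mL against a 100 mL target, assuming 1 to 5 more affected subjects on active, 200 to 400 mL/year of excess decline and 94 on active, and it is less once the retained FVC is used. The case rests on the inconsistency and on the low cost of removing it, not on these figures. Treatment policy is defined only for the primary FVC endpoint; for hospitalisation, death and SGRQ the argument rests on the intent-to-treat principle. The Visit 2 laboratory rule is a secondary matter of unclear wording.

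**What to change.** Reconcile Protocol 8.5.2 and 10.6 with 6.2, 10.5, 14.4.1 and Table 5:

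- State that a code break does not by itself end study follow-up.
- State that scheduled spirometry, SGRQ, hospitalisation and vital-status collection continue unless the subject withdraws consent.
- Flag FVC recorded after unblinding, and add to the SAP a sensitivity analysis that excludes it.
- State study-drug status after a code break separately. That is for the sponsor to set; no treatment rule is proposed here.
- In 10.3.1, say whether withdrawal after a Visit 2 laboratory result is from study drug or from the study, and reconcile it with the same sections.

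The cost is a few sentences in a protocol amendment, one data flag and a line in the SAP. No procedures are added, because the visits are already scheduled.

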8.6 Description of Investigational Agents

The planned dose levels (3 and 10 mg GB0139) have been selected in the original study design (Protocol version 5.1_UK) following review of non-clinical pharmacokinetic, safety pharmacology and toxicology data. Pharmacokinetic, toxicokinetic and toxicology studies in mice, rats and dogs indicate the drug is readily bioavailable via the inhaled route with little or no accumulation after 14-day dosing and is excreted in the faeces with a $t_{1/2}$ of approximately 6 h. Given the lack of adverse effects seen in the two species as well as the favourable safety profile seen in the phase I/IIa in healthy volunteers and IPF subjects, no direct anticipated adverse drug specific side effects are expected in the current study, nor are any drug interactions anticipated given the clear cytochrome profiling. Further details regarding non-clinical pharmacokinetic, safety pharmacology and toxicology data can be found in the IB.

8.7 Packaging and Labeling

The IMPs will be prepared by the sponsor and supplied to the Investigator. The Sponsor must ensure that the Investigator is notified prior to dispatch of IMP supplies, and of the anticipated date of their arrival. The IMP is shipped upon first screening, then arrives on site prior to dosing.

The IMPs must be received at each Investigational site by a designated person, handled and stored safely and properly, and kept in a secured location to which only the Investigator and designated staff have access. After a review of the temperature monitors included with shipments the Sponsor/CRO must ensure that it is confirmed that the transportation conditions were acceptable.

8.8 Storage, Handling, and Accountability

Following the Sponsor's approval, all remaining IMP will either be returned to the Sponsor or sent for destruction within 8 weeks of completion of the study-dosing period.

All used IMP containers and unused IMP will be held under quarantine in the investigator site facility pending accountability/return/destruction.

9.0 STUDY END POINTS

9.1 Primary Endpoint

- The annual rate of decline in Forced Vital Capacity (FVC; expressed in mL over 52 weeks).

9.2 Key Secondary Endpoints

- Proportion of subjects with an absolute decline from baseline in FVC (% pred) of $\leq 10\%$ at Week 52.
- Change from baseline in SGRQ total score at Week 52.
- Time to first hospitalization (respiratory related, including acute exacerbation of IPF).
- Time to death (all-causes).

9.3 Secondary endpoints

- Proportion of subjects with an absolute decline from baseline in FVC % pred of $\leq 5\%$ at w52.
- Change from baseline in 6-minute walk test (6MWT) distance over 52 weeks.
- Change from baseline in diffusion capacity of the lung for carbon monoxide (DLCO), corrected for HB, over 52 weeks.
- Change from baseline at week 52 for dyspnoea assessment by University of California San Diego - Shortness of Breath Questionnaire (UCSD - SOBQ).
- Change from baseline at week 52 for HRQoL as assessed by Short Form Survey (SF-36).
- Percentage of subjects with Adverse Events (AE) or Serious Adverse Events (SAE).
- Time to first hospitalization (IPF related, including acute exacerbation of IPF).
- Time to first hospitalization (all cause).
- Time to respiratory-related death.
- Time to initiation of nintedanib or pirfenidone.
- Change in FVC expressed in mL over 52 weeks for subjects who have never been treated with pirfenidone or nintedanib.

9.4 Safety Endpoints

- The following measure of safety will be assessing throughout the study:
 - Vital signs
 - Physical examination
 - Weight
 - Clinical laboratory tests (haematology, clinical chemistry and urinalysis)
 - Adverse events (see Section 11.0)
 - 12-lead electrocardiogram (ECG)

9.5 Exploratory Endpoints

9.5.1 Biomarkers

Change from baseline in selected biomarkers including but not limited to: YKL 40, PAI 1, PDGF-BB, MCP-1, CCL-18, KL-6, CA-125, CA-19, Gal-3 and collagen neoepitopes – described in [Appendix 2](#) (Section 18.0) – over time up to week 52 in all subjects.

9.5.2 Initiation or termination of nintedanib and pirfenidone in the previous stratified study population

9.5.3 Time to initiation of pirfenidone or nintedanib treatment for SoC2 participants up to the time when SoC1 and SoC2 were removed in the study. Pharmacogenetics

The study includes a pharmacogenetic component including but not limited to analysis of GAL-3 and IPF disease related genes of interest that might relate to the efficacy and/or safety of GB0139.

10.0 STUDY CONDUCT

This trial will be conducted in compliance with the protocol, Good Clinical Practice (GCP), applicable regulatory requirements, and International Conference on Harmonisation (ICH) guidelines.

10.1 Study Personnel and Organizations

The contact information for the project clinician for this study, the clinical laboratories, the coordinating investigator for each member state/country, the interactive voice response system (IVRS)/interactive web response system (IWRS) provider, the contract research organization (CRO) team may be found in the Investigator Site File. A full list of investigators is available in the sponsor's investigator database.

10.2 Arrangements for Recruitment of Subjects

Recruitment and enrollment strategies for this study may include recruitment from the investigator's local practice/hospital or referrals from other physicians. If advertisements become part of the recruitment strategy, they will be reviewed by the institutional review board (IRB)/independent ethics committee (IEC).

Enrollment strategies for this study may include the following:

- Review of local practice/hospital database
- Communication with other physicians/colleagues and cooperating health care facilities that regularly refer subjects for further diagnosis and care

